Participants: We will enroll 40 participants. As the narration of the VR device is only provided in English at this time, we require English proficiency for this pilot trial. Inclusion criteria: 1) ≥18 years old, 2) English proficiency; 3) receiving methadone treatment for DSM-5 confirmed OUD in the Montefiore network for at least 12 weeks, with no dose change in 14 days to ensure treatment stability; 4) chronic pain of at least moderate pain severity (score ≥4 on the Pain, Enjoyment of Life, and General Activity (PEG) scale); 5) willingness to participate in all study components; and 6) ability to provide informed consent, assessed using consent teach-back. Exclusion criteria: 1) conditions that could make participation in VR hazardous or cause adverse effects (current or prior diagnosis of epilepsy, seizure disorder, dementia, or migraines, any medical condition predisposing to nausea or dizziness, hypersensitivity to flashing light or motion), 2) conditions that could prevent proper use of the VR headset (stereoscopic vision or severe hearing impairment, or injury to eyes, face, or neck that prevents use of the VR headset), and 3) acute exacerbation of psychiatric conditions that preclude the ability to participate in the study. Pregnant patients are NOT excluded from the trial as there are no contraindications to their use of a VR device, but we are not specifically targeting pregnant patients for this study nor are we testing for pregnancy.

**Recruitment, Screening, and Randomization**. Recruitment will be active and passive in the OTP. Based on our team's prior DoSA trials and the scope of this current project, we anticipate enrolling 1-2

participants weekly. Research staff will enroll from one DoSA site for the duration of the trial; we will plan our recruitment strategy in conjunction with other IMPOWR-ME trials as to not recruit from the same pool of patients at a site at the same time. We expect retention of approximately 85% based on our groups prior DoSA trials.  **Screening:** After obtaining written consent, we will administer a screening questionnaire. Potentially eligible subjects will then complete a written informed consent process including discussion of procedures and risks and benefits before being randomized. Consent will occur in a private area of the OTP. **Randomization**: Randomization will occur using block randomization (blocks

of 4) to two conditions in a 1:1 ratio.

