**Data sources, measures, and management.** Study assessments will take place onsite at the OTP at weeks 0, 3, and 6 and last 30-60 minutes. Participants will receive \$50 compensation at each study assessment. We will track the number of patients screened, eligible, consented, and retained. During assessments, participants will answer surveys and submit saliva and blood. In addition, we will extract information from the Montefiore EMR, SMART EMR (methadone dosage), and from the New York State Prescription Monitoring Program (PMP). Study measures are listed in Table 1; where possible we align our measures with IMPOWR CDEs and with IMMPACT recommendations for study of chronic pain. All measures will be examined at each study visit, at 0, 3 and 6 weeks. All study assessment data will be managed in REDCAP, a well-established, HIPAA-compliant web-based surveying platform and database. During twice weekly VR sessions, we will also conduct before and after surveys to ask about experiences during VR exercises not taking more than 5 minutes; these will be paper based, scanned, and uploaded to Montefiore BOX, a HIPAA-compliant online cloud storage service. A portion of blood will also be bio-banked to facilitate future biomarker analyses. We will conduct an optional qualitative interview exploring experiences in the trial at the conclusion of the trial; participant interviews will be recorded and transcribed for analysis.

**Informed Consent.** The RA will screen all potential participants for inclusion and exclusion criteria in a private area of the MMTP. First, we will obtain written consent to administer a screening questionnaire. Screening questionnaire questions will focus on inclusion and exclusion criteria, pain history, and also ask about prior use of virtual reality devices. The initial screening questionnaire will take 15 minutes. Participants will not be reimbursed for the screening questionnaire. Written consent and the initial screening questionnaire will occur in a private area of the MMTP.

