**Analytic plan.** Feasibility: Feasibility outcomes will be measured as proportions. Preliminary Efficacy: To examine the association between treatment arm and the co-primary outcomes, we will use separate 2-level mixed-effects linear regression model with the treatment arm as a mixed effect with participant-specific random intercepts to account for hierarchical data. The difference in trends of pain intensity and opioid craving will be represented by the time-by-arm interaction. For secondary outcomes and stress and inflammation exploratory outcomes, we will use a similar strategy; where outcomes are dichotomous, we will use 2-level mixed effects logistic regression models.

We will use thematic analysis to analyze transcripts in the qualitative study.

**Power analysis**. The primary purpose of this study is to test feasibility and to generate preliminary data for a future R01 application. We are able to enroll 40 participants in the pilot RCT given our resources and given the time of this study. We base our conservative power analysis on t-tests of change in our pain intensity preliminary efficacy outcome and use effect size estimates from a study of RelieVRx. In that study, the pre-post difference in pain intensity was 2.2 in the treatment group and 1.2 in the control group. Given the effect size of d=0.49, and 20 participants in each arm, we will have 70% power to detect a difference of this magnitude or larger. We expect to have greater statistical power using mixed effects linear regression models with repeated measures over time.

**Risks/Benefits**. We expect the major risks to be associated with the VR technology. VR can sometimes cause "cybersickness" in some patients, especially when playing or experiencing fast moving games or videos. RelieVRx is a much less intense program designed to minimize these sensations. In the clinical trial of RelieVRx, about 10% of participants reported some nausea and/or motion sickness, but these symptoms were temporary and none decided to terminate their use of the technology because of adverse events. In our preliminary data of 20 patients, no patients have reported any issues with cybersickness. Nonetheless, this will be an important risk to discuss with patients.

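### With visits at weeks 0, 3 and 6, the planned time-by-arm test has essentially the same power as the t-test of change, so the expected repeated-measures gain is negligible and the 20-per-arm figure is not conservative

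*Combined protocol and SAP*

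**What the plan says.** The Power analysis paragraph under STUDY DESIGN states: "We base our conservative power analysis on t-tests of change in our pain intensity preliminary efficacy outcome". The inputs are the mean changes in a cited RelieVRx study, where "the pre-post difference in pain intensity was 2.2 in the treatment group and 1.2 in the control group", and the result is: "Given the effect size of d=0.49, and 20 participants in each arm, we will have 70% power". The paragraph closes with the expectation that the planned analysis will do better: "We expect to have greater statistical power using mixed effects linear regression models with repeated measures over time". It gives no size for that gain, no within-person correlation and no alpha.

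The Analytic plan specifies a two-level linear mixed model with treatment arm and participant-specific random intercepts. The tested term is the interaction: "The difference in trends of pain intensity and opioid craving will be represented by the time-by-arm interaction". Whether time is linear or categorical is not stated, although the word trends points to linear.

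The visit schedule is in the paragraph on data sources and measures: "All measures will be examined at each study visit, at 0, 3 and 6 weeks". The recruitment paragraph adds: "We expect retention of approximately 85% based on our groups prior DoSA trials".

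**The concern.** Repeated measures raise power only if the extra visits carry information about the contrast being tested. Here there is one extra visit, and it sits exactly midway between baseline and week 6. A slope fitted to three equally spaced points is determined by the two ends. The sentence about greater power therefore needs a calculation behind it, and there is none.

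The label conservative has a second difficulty. The t-test figure uses all 20 per arm, although the plan expects to keep about 85% of participants. A calculation that assumes no dropout is not a lower bound for an analysis that will have some.

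What is at stake is how the pilot is read and reused. The plan says the study is meant to produce preliminary data for an R01 application. If only the printed power figure were corrected, this sentence would still tell readers that the real analysis does better, and the same uncomputed allowance could pass into the next sample size.

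**Working it through.** **Inputs from the documents.** d = 0.49; 20 per arm; visits at 0, 3 and 6 weeks; random-intercept model with time-by-arm interaction; retention about 85%, so 0.85 × 20 = 17 completers per arm.

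**Assumptions.** Two-sided 5% (alpha is not stated). Arm and time main effects are in the model. Within-person correlation is 0.3 to 0.9 (not stated). The SD of change is scaled to 1, so the residual variance is 0.5, because Var(week 6 − week 0) = 2 × residual variance.

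**Step 1: the plan's own figure.** For the two-sample t-test of change:
- Variance of the difference = 2/20 = 0.100.
- Noncentrality = 0.49/√0.100 = 1.55.
- With 38 df, power = **32.7%** (45.1% if one-sided).

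The printed 70% is not reproduced. That is a separate point. What matters here is the comparison between the two tests.

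**Step 2: what the interaction estimates.** Centred times are −3, 0 and +3, with sum of squares 18. The slope weights are −3/18, 0 and +3/18. Multiplied by 6 weeks they become (−1, 0, +1). Generalised least squares gave the same weights at every within-person correlation tried. With complete data the six-week interaction is therefore the arm difference in mean (week 6 − week 0), the estimate the t-test uses. If time is categorical, the week-6 interaction is that same difference.

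**Step 3: its power with complete data.**
- Variance per arm = 0.5 × 36/(18 × 20) = 0.050, so the difference has variance 0.100, as in Step 1.
- Residual df = 120 observations − 40 participants − 2 slopes = 78.
- Noncentrality is again 1.55. With 78 df, power = **33.4%**.
- Gain: 33.4 − 32.7 = 0.7 points, all from the degrees of freedom. A 20,000-run simulation at correlation 0.6 gave 32.9% against 32.4%.
- For categorical time, the week-6 contrast gives 33.4%. The joint 2-df test does use week 3, but gives 25.5% if the effect grows linearly.

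**Step 4: 85% retention.** A t-test on 17 completers per arm has noncentrality 0.49/√(2/17) = 1.43 and 32 df, giving **28.3%**. The mixed model also uses the three dropouts per arm. Its variance is written below as an effective number of complete participants per arm; noncentrality is 0.49 × √(effective n/2).

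| Dropouts last seen at | df | Correlation | Effective n per arm | Power |
|---|---|---|---|---|
| week 3 | 72 | 0.3 | 18.10 | 30.7% |
| week 3 | 72 | 0.9 | 17.78 | 30.3% |
| baseline | 66 | 0.3 | 17.96 | 30.4% |
| baseline | 66 | 0.9 | 17.13 | 29.3% |

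The range is 29.3% to 30.7%, which is 1.0 to 2.4 points above the completer t-test. Every value is below the 32.7% of the 20-per-arm calculation.

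**Step 5: a model the text does not describe.** If the arm main effect is omitted, so that both arms share a baseline mean, complete-data power is 34.9% at correlation 0.9, 38.5% at 0.7, 43.4% at 0.5 and 50.4% at 0.3.

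**The case against.** The strongest reply is that the sentence promises only more power, not how much, and that in a like-for-like comparison it is true in direction: 33.4% against 32.7% with complete data, and 29.3% to 30.7% against 28.3% at 85% retention. That stands. A reader might infer that the gain is nil, or that the planned test ignores week 3. Neither follows. The zero weight belongs to the complete-data point estimate. Week 3 still enters the residual variance and degrees of freedom, and with dropout it enters the estimate as well. In one fitted example, adding 5 points to every week-3 value in one arm left the six-week estimate at 0.5855 but moved its standard error from 0.28 to 0.98.

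A second reply is that setting the model with dropout against a t-test without dropout compares unlike things. That also stands as far as the model's merit goes: the 2 to 3 point shortfall from 32.7% is due to attrition, not to the mixed model. It does bear on the label conservative, because the no-dropout calculation is the one given that label.

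Third, the plan leaves the fixed effects and the coding of time partly open, and a common-baseline model would gain noticeably more (Step 5). True, but the Analytic plan places arm in the model and does not mention a shared baseline.

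Finally, the consequence is limited. The study is primarily a feasibility pilot, its size is set by resources and time, and nothing in the documents says the argument will be reused for the R01.

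**Conclusion.** The point holds in a limited form. For the model as written, the power gain over the t-test of change is negligible: 0.7 points with complete data and 1.0 to 2.4 points over a completer t-test at 85% retention. The 20-per-arm t-test is not a lower bound for the planned analysis at the plan's own retention. The label conservative and the expectation of materially greater power are therefore unsupported.

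This rests on d = 0.49, two-sided 5%, arm and time main effects, a random intercept as the true covariance, and correlation between 0.3 and 0.9. If true slopes vary between participants, the random-intercept test can look more powerful, but only with an inflated type I error: 6.6% and 9.5% in simulation when 25% and 50% of the variance of change is slope variance.

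A reader might also set about 30% against the printed 70% and count some 40 points as the size of this finding. The documents do not support that: nearly all of the gap is the separate error in the 70%, which would remain whichever of the two tests were used.

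**What to change.** In the Power analysis paragraph, delete the word conservative and the sentence on greater power from the mixed model. Suggested replacement:

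*With assessments at weeks 0, 3 and 6 and complete data, the time-by-arm contrast in the planned random-intercept model equals the difference in mean six-week change. Its power is therefore essentially that of the t-test of change: about 33% with complete data and about 30% at 85% retention, for d=0.49 and a two-sided 5% level.*

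The sponsor should confirm the alpha and state how time is coded. If a common-baseline model is intended, specify it in the Analytic plan and compute its power for that model: about 35% to 50% with complete data for correlation 0.9 down to 0.3, still well short of 70%. Do not carry a repeated-measures gain into the R01 sizing unless it has been computed for the model and contrast to be used.

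The cost is wording in one paragraph, with no change to participants, visits or data. The drawback is a less favourable power statement.

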| Illicit opioid use and             | Modified Addiction severity index  , Narcan use and   | S             |
| substance use                      | overdose   |               |
| Prescription opioid use            | Opioid prescriptions, including methadone dose   | S, EMR
PMP |
| Sociodemographics                  | Age, gender, insurance, race/ethnicity, education, marital status, socioeconomic status, social support  , social risk assessment questionnaire | S             |
| Perceived discrimination           | Adapted perceived discrimination scale    | S             |
| Mindfulness                        | Mindful attention awareness scale   | S             |
| Technology Attitudes               | VR Knowledge, Media and Technology Use and Attitudes subscale   | S             |
| Stress and Inflammation            |  |               |
| Cortisol                           | Morning salivary cortisol, serum morning cortisol  | L             |
| C-reactive protein                 | Serum CRP  | L             |
| Cytokine panel                     | Serum cytokines  | L             |
| Before/After VR Surveys            |  |               |
| Pain                               | Pain intensity score   | S             |
| Mood                               | Brief Mood Introspection Scale    | S             |
| Mindfulness                        | State Mindfulness Scale   | S             |
| Immersion & Distraction            | Adapted Immersion Scale  , Adapted Distraction Scale   | S             |

and executive functioning and attentional games to strengthen pain coping skills. RelieVRx is typically delivered in a 56-day program through daily virtual experiences, with each experience lasting between 2 and 16 minutes; in this pilot study, we will conduct in-office virtual experiences twice weekly. Each session will last about 20-30 minutes and go through 1-5 virtual experiences. The sham VR control is a non-immersive set of 56 daily virtual experiences, tuned to the length of the RelieVRx. Control participants will similarly experience 1-5 virtual experiences in each 20-30 session.

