Another risk is breach of confidentiality of patient data. Such a breach is unlikely, because all study staff will be trained in confidentiality and secure data management, and the data collected as part of this study will be stripped of protected health information.

In the major clinical trials of RelieVRx, both intervention and sham VR groups had reduced pain at the end of the trial, with the magnitude being larger in the intervention arm. However, this trial is shorter and some of the parameters are not the same, including the number of weeks of the intervention. Therefore, it is possible, but not certain, participants will receive a direct benefit.

**Data Safety Monitoring Plan**. Monitoring of recruitment and retention, adverse events, protocol deviations, and protocol violations will be ongoing by the Principal Investigator. Additionally, the PI and co-investigators will meet every 2 months in person to discuss recruitment, retention, data quality, and any adverse events. Together, they will make corrective plans as necessary. No interim analyses are planned for this pilot trial.

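### Cybersickness is the only VR risk the protocol describes, yet no structured collection of VR symptoms, and no summary of them by arm, is specified

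*Combined protocol and SAP*

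**What the plan says.** All places are in the Study Design section of the combined protocol and SAP.

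- **Risks/Benefits.** "We expect the major risks to be associated with the VR technology". Cybersickness is the only VR risk then described. For the earlier RelieVRx trial, "about 10% of participants reported some nausea and/or motion sickness"; those symptoms were temporary and nobody stopped use because of adverse events. For the team's own experience: "In our preliminary data of 20 patients, no patients have reported any issues with cybersickness". The follow-up stated is that the risk will be discussed with patients.
- **Data sources, measures, and management.** At the twice-weekly sessions "we will also conduct before and after surveys to ask about experiences during VR exercises not taking more than 5 minutes". These are paper forms.
- **Table 1.** The before/after survey has four domains: pain intensity, mood ("Brief Mood Introspection Scale"), state mindfulness, and immersion and distraction (adapted scales). The measures for weeks 0, 3 and 6 include no row for cybersickness, nausea, dizziness, tolerability or adverse events.
- **Data Safety Monitoring Plan.** "Monitoring of recruitment and retention, adverse events, protocol deviations, and protocol violations will be ongoing by the Principal Investigator", with a team meeting every 2 months. How events are asked about, graded or recorded is not stated.
- **Analytic plan.** It covers feasibility proportions, efficacy, biomarkers and qualitative data. It contains no safety summary.

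**The concern.** The protocol identifies a specific, foreseeable risk and already hands every participant a form immediately before and after each exposure, but that form has no listed domain for the risk. The same instrument goes to both arms, so it is the natural place for a comparison of immersive with non-immersive VR.

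At stake is what the pilot can say about tolerability. Its stated purpose is feasibility and preliminary data for a larger application. Without a defined way of collecting symptoms, a count of zero or one could reflect good tolerability or incomplete capture, and a difference between arms could reflect who happened to be asked. Outside data do not settle the matter. The usual programme is daily experiences of 2 to 16 minutes, whereas here 1 to 5 experiences are combined in a sitting of 20 to 30 minutes. The protocol itself says that some parameters differ from the earlier trials.

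**Working it through.** The documents state no precision or detection figure for cybersickness, so there is none to reproduce. The following is an illustration.

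**Inputs**
- Participants per arm: n = 20 (Power analysis: "20 participants in each arm"). With expected retention of about 85% (Recruitment paragraph), 0.85 × 20 = 17.
- True participant-level rate: p = 10%, from Risks/Benefits. That figure is not split by arm and is itself a reported rate. Applying it to the RelieVRx arm is an assumption, so 5% and 15% are shown too.
- Share of true cases that get recorded: s. The documents give no value; 25% to 100% is an assumed range.

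**Chance that no case is recorded**

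P(none) = (1 − p × s)^n, with participants independent.

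For p = 10% and n = 20:
- s = 100%: 0.90^20 = 12.2%
- s = 75%: 0.925^20 = 21.0%
- s = 50%: 0.95^20 = 35.8%
- s = 25%: 0.975^20 = 60.3%

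| p, n | s = 100% | 75% | 50% | 25% |
|---|---|---|---|---|
| 5%, 20 | 35.8% | 46.6% | 60.3% | 77.8% |
| 10%, 20 | 12.2% | 21.0% | 35.8% | 60.3% |
| 15%, 20 | 3.9% | 9.2% | 21.0% | 46.6% |
| 10%, 17 | 16.7% | 26.6% | 41.8% | 65.0% |

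The expected number of true cases at 10% is 0.10 × 20 = 2.

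**What a zero would mean**

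The exact upper limit for 0 of 20 is 1 − 0.05^(1/20) = 13.9% (one-sided 95%) or 1 − 0.025^(1/20) = 16.8% (two-sided 95%). This holds even with complete capture. It applies equally to the preliminary 0 of 20, which does not exclude a rate of 10%.

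**Opportunities to ask**

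6 weeks × 2 sessions × 20 participants = 240 after-session surveys per arm. This is a ceiling that assumes full attendance.

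**Why a threshold is needed**

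Suppose 5% of sessions show a chance rise of one point (assumption), independently across 12 sessions. Then 1 − 0.95^12 = 46% of participants would be flagged at least once, which would swamp a 10% signal. Counting any increase would therefore be a poor summary.

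**The case against.** The strongest reply is that the gap is one of documentation, and small. Adverse events are monitored on an ongoing basis and reviewed every 2 months, and participants are seen in person twice a week. The exclusion criteria remove people with conditions predisposing to nausea or dizziness, migraines, seizure disorders, or hypersensitivity to flashing light or motion, so the rate may be below 10%. An optional end-of-trial interview may catch some cases. Tolerability is not among the stated feasibility outcomes. All of this stands, but none of it is a common, prompted measure in both arms.

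A reader might also infer more than the documents support:

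- *That the trial relies on volunteered complaints.* The protocol does not say whether adverse events are prompted. The supportable statement is that no structured collection is specified.
- *That no instrument asks about symptoms.* The items of the adapted immersion and distraction scales are not shown. What can be said is that no such domain is listed.
- *That missed symptoms would hide a cause of skipped sessions or dropout.* The only evidence given points the other way: in the earlier trial nobody stopped because of adverse events.
- *That the trial will wrongly declare cybersickness absent.* No conclusion on cybersickness is planned.

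**Conclusion.** The point holds as a gap in safety measurement: no structured symptom collection and no by-arm summary for the one VR risk the protocol describes. It is a cheap improvement and not a flaw in the efficacy analysis; the co-primary outcomes are untouched.

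Only the 12% figure avoids an assumed capture rate, and it still takes the earlier trial's rate as the true rate in this arm. The range of 21% to 60% also depends on capture of 75% down to 25%, so no single value in it, such as 36% at half capture, should be cited as the plan's error. Nor should a reader infer that prompting cures the problem: with 20 per arm, about one trial in eight would still record no case at a true 10%. Hence the need for exact limits alongside any count. No claim about dropout is made.

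**What to change.** - Add a brief nausea/dizziness item to the existing before and after session survey in both arms. The before score separates existing symptoms from those arising during VR.
- Pre-specify what counts as a meaningful increase, so that a one-point rise does not qualify by itself.
- Report by arm the number of participants ever meeting the threshold, with exact 95% intervals, including the upper limit if the count is zero. Report the number of sessions meeting it out of sessions attended, descriptively, because sessions within a person are not independent.
- State in the Data Safety Monitoring Plan how adverse events are elicited and recorded, in the same way for both arms.

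The cost is a few seconds per session, a minor amendment and some added mild reports. Sessions already held without the item cannot be recovered; if enrolment has begun, report how many sessions preceded the change.
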